## 2.2 Protocol Deviations

Only important protocol deviations (PDs) will be listed and tabulated in the CSR, and only for randomised participants (not screening failures). These are defined as PDs which may significantly affect the completeness, accuracy and/or reliability of the study data, or which may significantly affect a participant's rights, safety, or well-being. Important PDs in this trial will be grouped under one of the following categories:

- Did not fulfill key eligibility criteria
- Discontinuation criteria for study product met, but participant not withdrawn from study treatment
- Discontinuation criteria for overall study withdrawal met but patient not withdrawn from study
- Investigational product (IP) deviation
- Excluded medications taken
- Deviations related to study procedure
- Other important deviations

Important protocol deviations associated with the global/county situation will also be summarised separately (see Section 4.2.13).

Important PDs will be identified and documented by the study team prior to unblinding of the trial at the primary database lock. As far as possible, the occurrence of important PDs will be monitored (blinded) during the trial, with the emphasis on their future prevention.

With the exception of the PK analyses, important PDs will not be used to exclude any participant from any analysis set, nor to exclude any data from participants included in an analysis set.

The study non-compliance handling plan outlines the management of PDs and includes the proposed specific categories of PDs in this trial. Any PDs which are not defined as important will not be reported and discussed in the CSR.

## 3 PRIMARY AND SECONDARY VARIABLES

### 3.1 General Definitions

#### 3.1.1 Definition of Baseline

In general, the last non-missing measurement on or prior to the date of randomisation will serve as the baseline measurement for efficacy variables. If there is no value on or prior to the date of randomisation, then the baseline value will be set to missing.

In general, the last non-missing measurement prior to first dose of study treatment will serve as the baseline measurement for safety variables. If there is no value prior to first dose of study treatment, then the baseline value will be set to missing.

Where unscheduled/repeat assessments are relevant and exist for any participant at a particular visit specified below, they will also be considered in the baseline definitions, provided they remain prior to the date of randomisation (efficacy) or the date of first dose of study treatment (safety).

For the NPSD (NCS included), the baseline is the average of daily responses from Day -13 to Day 0. The mean is calculated as the sum of all non-missing daily scores over these 14 sequential days divided by the number of non-missing daily scores. If more than 7 daily scores (>50%) within the baseline period are missing, then baseline is set to missing.

Of note, Day 0 is Day 1 in the analysis following the Clinical Data Interchange Standards Consortium (CDISC) standards (Section 3.1.4), although it is labelled as Day 0 in the CSP.

### 3.1.2 Absolute Change from Baseline

Absolute change from baseline is defined as (*post-baseline value – baseline value*).

If either the post-baseline value or the baseline value is missing, then the absolute change from baseline will also be missing.

Unless otherwise specified, “change from baseline” is assumed to be the absolute change from baseline.

### 3.1.3 Study Periods

The following study periods are defined for analysis purposes:

- **Screening/run-in period:** starting on the date of the first study procedure and ending one day prior to randomisation (for randomised participants) or on the date of the last study procedure (for screening failures). If any participant is re-screened, the latest available screening will be used for this purpose.
- **Planned treatment period:** starting on the date of randomisation (efficacy) and ending on the date of the Week 52 visit or earlier study withdrawal date (for participants not followed up until Week 52). Unless noted otherwise, efficacy analyses will be based on planned treatment period.
- **On-treatment period:** starting on the date of first dose of IP and ending on the earlier (date of last dose of IP + 33 days, date of study withdrawal). Note: The 33 days is derived as dose frequency (28 days) plus 5 days as specified in the CSP Section 1.3.

- **Post-treatment period:** starting on the day after the end of the on-treatment period until the end of the study (Week 76 for the first ~200 participants and Week 64 for the remaining participants) or early withdrawal date.
- **On-study period** (planned treatment and follow-up): starting on the date of randomisation (efficacy) / date of first dose of IP (safety) and ending on the study completion or withdrawal date. For analyses performed at primary database lock, the on-study period is understood to include all data recorded up until the date of the data cut-off for the primary database lock (which includes all follow-up data available at the time of the data cut-off).
- **Additional FU period:** starting on the day after Week 64 visit until the end of the study (Week 76) or early withdrawal date. Only the first ~ 200 participants will continue follow-up beyond Week 64.

If a participant dies, the end dates of the study periods defined above will be capped at the date of death.

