Data presentation	08Feb2023	PK analysis set definition updated to clarify that at least one detectable tezepelumab serum concentration for a sample collected post-treatment is required (Section 2.1.3).	Yes CSP v5.0	To align with the CSP v5.0.
Data presentation	08Feb2023	Additional FU analysis set has been added (Section 2.1.3).	N/A	To be used for AE summaries.
Data presentation	08Feb2023	The title of Section 2.2 and categories of important PDs updated (Section 2.2).	N/A	To be align with Non-compliance handling plan v4.0.
Data presentation	08Feb2023	Reference to the date of first dose of IP for safety analysis purpose removed from planned treatment period (Section 3.1.3).	N/A	Planned treatment period is used only for efficacy analyses.
Data presentation	08Feb2023	Additional FU period has been added (Section 3.1.3).		To be used for AE summaries.
Data presentation	08Feb2023	Clarification provided that Day 0 in the CSP is equal the Day 1 according to the CDISC standard (Section 3.1.4).	N/A	To align with CDISC standards.
Data presentation	08Feb2023	The upper limit for CT scan visit window updated from 378 to 490 (Section 3.1.4).	N/A	To allow for CT scans done by the end of Week 64 to be included in the analysis.
Data presentation	08Feb2023	To clarify that subgroups are based on all data at the study entry or at baseline (Section 3.1.6).	N/A	To provide clarification of subgroups definition.
Data presentation	08Feb2023	Perennial specific IgE status will be based on 7 (and not 8) panels (Section 3.1.6).	N/A	IgE Oriental Cockroach panel will not be assessed.
Data presentation	08Feb2023	Baseline Ethmoid / Maxillary ratio has been defined as the additional baseline characteristic (Section 3.1.7).	N/A	To provide information of interests.
Data presentation	08Feb2023	The FEV 1 assessment flagged as the best value according to DTS will be used in analysis (Section 3.3.6).	N/A	To provide clarification which FEV 1 assessment should be used in analysis.

Data presentation	08Feb2023	The Health State Index has been added as part of EQ-5D-5L presentation (Sections 3.5.2 and 4.2.9.3 ).	N/A	To be align with EQ-5D-5L presentation across the tezepelumab project.
Data presentation	08Feb2023	The denominator for presenteeism, work productivity loss and activity impairment updated from 6 to 10 (Section 3.5.5 SAP v2.0).	N/A	To correct the derivation of WPAI outcome measures.

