### 3.1.4 Visit Windows

All summaries and analyses, both efficacy and safety, which are presented by time point (e.g. “Week 52”) will use a visit window to classify the data record, which is derived from the assessment date relative to the reference start date. This approach allows appropriate classification of visits which may have occurred significantly earlier or later than the protocol assessment schedule, as well as the use of data captured at visits which have no fixed timing (notably the IPD visit), and the handling of data captured at visits for which the database label is incorrect and unresolvable.

Nominal database visit numbers will not be used in any summary or analysis by visit.

For Screening/run-in period, the relative day is defined as (Date of assessment – Date of randomization).

For periods after randomization:

For efficacy variables, the reference start date is the date of randomisation, and relative day is therefore defined as (Date of assessment – Date of randomisation) + 1.

For safety variables, the reference start date is the date of first dose of IP, and relative day is therefore defined as (Date of assessment – Date of first dose of IP) + 1.

Any data collected at unscheduled or repeat visits will be listed and will be included in baseline definitions (see Section 3.1.1), and in any definitions of maximum value, minimum value or last value within the relevant study period.

Data collected at unscheduled or repeat visits will also be included in visit windows, and therefore may be included in summaries or analyses by visit or used in any sensitivity analyses which involve imputation of data from participants with non-missing values to participants with missing values. In the case of a missing value at a scheduled visit, which is then followed by a non-missing value at an unscheduled or repeat assessment within the same visit window, the non-missing value at the unscheduled/repeat assessment will replace the missing value at the scheduled visit.

If a participant has more than one non-missing value within the same visit window, the following rules will apply:

- The non-missing value closest to the target day will be selected for analysis at that visit.
- If two non-missing values are equidistant from the target day, the earlier of the two values will be selected for the analysis at that visit.

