- If two non-missing values are recorded on the same day and have a different assessment time, the value with the earliest assessment time will be selected for analysis at that visit.
- If two non-missing values (for continuous variables) are recorded on the same day and have no assessment time associated with at least one of them, or the same assessment time associated with both of them, the average of the two values will be selected for analysis at that visit. For categorical variables in this situation, the worst case will be used.
- If there are multiple ADA samples in the same visit window with both positive and negative results, the sample with a positive result and the highest titre value will be selected.

If a participant has no value within a particular visit window, then the participant will have a missing value at that visit in summaries and analysis.

The same visit window definitions below will be used regardless of whether the planned treatment period or the on-treatment period is used for analysis (see Section 3.1.3). In practice, each data record in the planned treatment period will be first identified, and then further flagged according to whether it is on-treatment or off-treatment. This flag will be used to select all eligible records for subsequent visit windowing, according to whether the derived visits are to be used in a planned treatment period or an on-treatment period analysis. It should be noted that, if treatment was discontinued within a particular visit window, the rules above for handling multiple values within the same visit window could select a different record according to whether a planned treatment period analysis or an on-treatment period analysis is needed.

**Table 1** summarises the visit windows to be used for all variables unless specified otherwise. It corresponds to the full (mostly 4-weekly) protocol scheduling for clinic visits and will be

used for all variables by default, including those variables which are not capture at every clinic visit, unless indicated below that the visit windows in [Table 2](#) or [Table 3](#) should be used. Of note, Week 0 is Day 1 in the analysis following the Clinical Data Interchange Standards Consortium (CDISC) standards, although it is labelled as Day 0 in the CSP.

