**Table 3 Visit Windows – NPSD (including NCS)**

Time Point	Target Day	Visit Window
Baseline (Week 0)	See Section 3.1.1 for baseline definitions	
Week 2	15	2-15
Week 4	29	16-29
Week 6	43	30-43
...	...	...
Week 52	365	352-365
...	...	...
Follow-up	533	520-533
Week 76		

In all cases above, no time points will be presented in summary tables or included in statistical analysis which do not correspond to the time points scheduled in the protocol for the variable in question.

For CT scan, the visit window for Week 52 will include Days 1 – 490.

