### **3.2.2 Change from baseline in nasal congestion score at Week 52**

Participant reported nasal congestion (NC) will be evaluated as part of the NPSD. The NCS (nasal congestion score) is captured by one item in the NPSD asking participants to rate the severity of their worst NC over the past 24 hours using the following response options: 0 – None; 1 – Mild; 2 – Moderate; 3 – Severe. Baseline will be the mean of daily responses from Day -13 to Day 0. Bi-weekly (14-day) mean NCS will be calculated if at least 8 days in each 14-day period has evaluable data; otherwise the bi-weekly mean is set to missing. The NCS and the changes from baseline at Week 52 will be calculated for the co-primary efficacy endpoint.

Additional, based on the Meaningful Change Thresholds (MCT) reported in Shih et al., 2023, participants with change from baseline in bi-weekly mean NCS  $\leq$  -1.0 will be defined as NCS responders.

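### Does ending the planned treatment period on the Week 52 visit date cut the Week 52 diary interval short?

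*SAP*

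**What the plan says.** SAP 3.1.3 sets the planned treatment period as "starting on the date of randomisation (efficacy) and ending on the date of the Week 52 visit or earlier study withdrawal date", and adds: "Unless noted otherwise, efficacy analyses will be based on planned treatment period".

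SAP 3.1.4 opens with a general rule for anything presented by time point: such analyses "will use a visit window to classify the data record, which is derived from the assessment date relative to the reference start date". Later in the section, where it separates on-treatment from off-treatment data, it says: "In practice, each data record in the planned treatment period will be first identified, and then further flagged" and then "This flag will be used to select all eligible records for subsequent visit windowing".

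Table 3 gives the congestion score and the other diary items a Week 52 target of Day 365 and a window of Days 352-365. SAP 3.2.2 requires 8 days: "Bi-weekly (14-day) mean NCS will be calculated if at least 8 days in each 14-day period has evaluable data". SAP 1.2 and the protocol's Schedule of Activities allow the Week 52 visit within 5 days either side. Protocol 8.1.2.1 has the diary completed daily through follow-up, so entries after an early visit normally exist.

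For CT, SAP 3.1.4 states: "For CT scan, the visit window for Week 52 will include Days 1 – 490". The amendment history gives the reason: "To allow for CT scans done by the end of Week 64 to be included in the analysis".

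**The concern.** If the steps in 3.1.4 are taken strictly in order, records after the Week 52 visit are removed first and only the remainder is windowed. A participant seen five days early would then lose the last five diary days of the Week 52 interval although those entries were collected. They would not be used elsewhere either: on Table 3's 14-day pattern the next interval starts on Day 366. Some participants would fall below 8 days and move from observed to imputed. No sentence exempts the diary from this order. The cut-off date is not even unique, because Protocol 1.3 (Order of Assessments) lets the end-of-treatment assessments run over more than one day. The interval feeds one co-primary and two key secondary endpoints, and a confirmatory derivation should have a single reading.

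**Working it through.** **Table 3 reproduced.** Target day for Week 52 = 52 × 7 + 1 = 365. A 14-day block ending there runs from 365 − 13 = 352 to 365. The same rule returns the other printed rows: Week 2, 2-15; Week 4, 16-29; Week 6, 30-43; Week 76, 520-533. The visit window is 365 ± 5, or Days 360-370.

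**Diary days left on the strict reading.** Days kept = min(visit day, 365) − 352 + 1. Missed entries tolerated = days kept − 8.

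| Visit day | Days kept | Misses tolerated |
|---|---|---|
| 360 | 9 | 1 |
| 361 | 10 | 2 |
| 362 | 11 | 3 |
| 363 | 12 | 4 |
| 364 | 13 | 5 |
| 365-370 | 14 | 6 |

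Every visit inside the window leaves at least 9 days, so the 8-day minimum can still be met.

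**Extra missing Week 52 scores.** The documents give neither expected diary completion nor the spread of visit dates, so both are assumptions here. With independent daily completion q and d days kept, P(missing) = P(Bin(d, q) ≤ 7), against P(Bin(14, q) ≤ 7) with the full window. The table averages the difference over visit days, in percentage points. Triangular weights are 6 − |day − 365|.

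| q | Visits on Days 364-366 | Triangular around Day 365 | Even over Days 360-370 |
|---|---|---|---|
| 95% | 0.00 | 0.3 | 0.8 |
| 90% | 0.02 | 1.2 | 2.9 |
| 80% | 0.6 | 5.4 | 9.9 |

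Protocol 8.1.2 has an outstanding entry completed on site at the visit. If the visit-day entry is therefore always present, the rows become 0.00 / 0.2 / 0.6, 0.01 / 1.0 / 2.3 and 0.4 / 4.4 / 8.3. The largest table entry, 9.9 points, is about 20 of 200 participants per arm. The 70% in Protocol 5.1 is a minimum for entry, not an expected level during treatment.

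**Power.** From SAP 1.3: difference 0.87, SD 1.22, 2-sided 1% level. Standard error = 1.22 × √(2/n). At n = 200 it is 0.122, the ratio is 0.87 / 0.122 = 7.13, and power = Φ(7.13 − 2.576) = 0.999997. At n = 180, treating 20 per arm as simply lost, the standard error is 0.1286, the ratio is 6.77 and power is 0.99999.

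**Which reading the text supports.**

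- The opening rule of 3.1.4 covers all time-point analyses and classifies a record by its own date relative to randomisation. The same section sets nominal visit labels aside and says the approach is meant to cope with visits well off schedule. Letting one clinic date decide which home-diary days count runs against that.
- The period default in 3.1.3 yields where something else is noted, and Table 3 notes Days 352-365.
- The sentence about identifying records before windowing them sits in a paragraph about the on-/off-treatment flag. That paragraph begins by saying the same windows apply whichever period is analysed.
- The CT window to Day 490 was set so that scans well after the Week 52 visit count. The Week 52 windows in Tables 1 and 2 also run past Day 370, to Days 378 and 406. This is weaker evidence, since a late visit could itself fall there.
- SAP 4.2.6.1 Step 1 lists what blanks a bi-weekly score: surgery, or systemic corticosteroid or biologic use for polyps. An early clinic visit is not among them.

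**The case for a change.** The best case for a change is that intent is being inferred. CT received an explicit window and the diary received no statement that its window overrides the period end, so two programmers could derive different Week 52 scores. Missingness also has consequences in this SAP apart from power. Section 4.2.6.4.3 triggers a tipping-point analysis when more than 5% in either arm are missing at Week 52, and 4.2.6.5 leaves participants with missing values out of the distribution curves. At an assumed 80% completion with the visit-day entry secured, the strict reading gives 5.3% (triangular) or 9.2% (even) missing from diary gaps alone, against 0.9% with the full window, so it could trip that trigger by itself. SAP 2.1.4 rules out updates after primary database lock.

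The gap in the wording stands: nothing expressly exempts the diary. The consequences do not amount to much. The trigger adds a sensitivity analysis; it does not alter the primary result. Reaching it this way needs both the less likely reading and completion near 80% with widely scattered visits. Protocol 8.1.2 requires at least weekly adherence checks precisely to protect the co-primary data. Participants who discontinued treatment hand back the diary at the end-of-treatment visit (Protocol 7.1.1), so for them an added sentence would recover nothing. A diary-only exemption might also suggest that other variables are cut at the visit date.

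**Conclusion.** The point is a small gap in wording that analysts would fill sensibly by using Days 352-365 for the Week 52 diary interval. The period rule and Table 3 are not in conflict: they can be applied in sequence, and the surrounding text favours the full window. If the strict reading were programmed anyway, 9-13 diary days would remain for visits on Days 360-364 and all 14 for later ones. The cost would be 0-0.8 points of extra missing scores at 95% completion, 0-2.9 at 90%, and up to 9.9 at 80% with evenly spread visits. These sizes rest on assumed completion, independent misses and assumed visit timing. Power is essentially untouched, and no mechanism is apparent by which visit timing would differ by arm. The trial's conclusion would be sound on either reading, so a clarifying sentence would only record what would be done in any case. No change is needed.

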### 3.1.4 Visit Windows

All summaries and analyses, both efficacy and safety, which are presented by time point (e.g. “Week 52”) will use a visit window to classify the data record, which is derived from the assessment date relative to the reference start date. This approach allows appropriate classification of visits which may have occurred significantly earlier or later than the protocol assessment schedule, as well as the use of data captured at visits which have no fixed timing (notably the IPD visit), and the handling of data captured at visits for which the database label is incorrect and unresolvable.

Nominal database visit numbers will not be used in any summary or analysis by visit.

For Screening/run-in period, the relative day is defined as (Date of assessment – Date of randomization).

For periods after randomization:

For efficacy variables, the reference start date is the date of randomisation, and relative day is therefore defined as (Date of assessment – Date of randomisation) + 1.

For safety variables, the reference start date is the date of first dose of IP, and relative day is therefore defined as (Date of assessment – Date of first dose of IP) + 1.

Any data collected at unscheduled or repeat visits will be listed and will be included in baseline definitions (see Section 3.1.1), and in any definitions of maximum value, minimum value or last value within the relevant study period.

Data collected at unscheduled or repeat visits will also be included in visit windows, and therefore may be included in summaries or analyses by visit or used in any sensitivity analyses which involve imputation of data from participants with non-missing values to participants with missing values. In the case of a missing value at a scheduled visit, which is then followed by a non-missing value at an unscheduled or repeat assessment within the same visit window, the non-missing value at the unscheduled/repeat assessment will replace the missing value at the scheduled visit.

If a participant has more than one non-missing value within the same visit window, the following rules will apply:

- The non-missing value closest to the target day will be selected for analysis at that visit.
- If two non-missing values are equidistant from the target day, the earlier of the two values will be selected for the analysis at that visit.
- If two non-missing values are recorded on the same day and have a different assessment time, the value with the earliest assessment time will be selected for analysis at that visit.
- If two non-missing values (for continuous variables) are recorded on the same day and have no assessment time associated with at least one of them, or the same assessment time associated with both of them, the average of the two values will be selected for analysis at that visit. For categorical variables in this situation, the worst case will be used.
- If there are multiple ADA samples in the same visit window with both positive and negative results, the sample with a positive result and the highest titre value will be selected.

If a participant has no value within a particular visit window, then the participant will have a missing value at that visit in summaries and analysis.

The same visit window definitions below will be used regardless of whether the planned treatment period or the on-treatment period is used for analysis (see Section 3.1.3). In practice, each data record in the planned treatment period will be first identified, and then further flagged according to whether it is on-treatment or off-treatment. This flag will be used to select all eligible records for subsequent visit windowing, according to whether the derived visits are to be used in a planned treatment period or an on-treatment period analysis. It should be noted that, if treatment was discontinued within a particular visit window, the rules above for handling multiple values within the same visit window could select a different record according to whether a planned treatment period analysis or an on-treatment period analysis is needed.

**Table 1** summarises the visit windows to be used for all variables unless specified otherwise. It corresponds to the full (mostly 4-weekly) protocol scheduling for clinic visits and will be

used for all variables by default, including those variables which are not capture at every clinic visit, unless indicated below that the visit windows in [Table 2](#) or [Table 3](#) should be used. Of note, Week 0 is Day 1 in the analysis following the Clinical Data Interchange Standards Consortium (CDISC) standards, although it is labelled as Day 0 in the CSP.

